##### Pregnancy

Pregnancies and suspected pregnancies (including a positive pregnancy test regardless of age or disease state) of a female subject or a female partner of a male subject occurring while the subject is on study, or within the period stipulated for continued contraceptive use for WOCBP (5 months) and sexually active men (6 months) after the subject's last dose of study medication should be recorded as SAEs. The female subject is to be discontinued immediately from the study for a pregnancy event.

For Affiliate sites, the pregnancy, suspected pregnancy, or positive pregnancy test must be reported to the Multicenter Project Manager immediately (within 24 hours) at [contact] (primary route of submission) or [contact] (back-up)). The Multicenter Project Manager will then report the event to the Funding Source (see requirements below). The female subject or the female partner of a male subject should be referred to an obstetrician-gynecologist, preferably one experienced in reproductive toxicity for further evaluation and counseling.

The Investigator will follow the female subject or female partner of a male subject until completion of the pregnancy, and must document the outcome of the pregnancy (either normal or abnormal outcome) and report the condition of the fetus or newborn to the Multicenter Project Manager. If the outcome of the pregnancy was abnormal (e.g., spontaneous or therapeutic abortion), the Investigator should report the abnormal outcome as an AE. If the abnormal outcome meets any of the serious criteria, it must be reported as an SAE.

Note if the female subject or female partner of a male subject has received nivolumab, the investigator must immediately notify Worldwide Safety @BMS of this event via the Pregnancy Surveillance Form in accordance with SAE reporting procedures. The nivolumab IB notes that non-clinical safety findings of adverse pregnancy outcomes and infant losses in the absence of maternal toxicity have been reported. Findings in monkeys suggest a potential risk to human pregnancy if there is continued treatment with nivolumab during pregnancy.

### Laboratory Test Abnormalities

The following laboratory abnormalities should be documented and reported appropriately:

- any laboratory test result that is clinically significant or meets the definition of an SAE
- any laboratory abnormality that required the subject to have study drug discontinued or interrupted
- any laboratory abnormality that required the subject to receive specific corrective therapy.

### Overdose

An overdose is defined as the accidental or intentional administration of any dose of a product that is considered both excessive and medically important. All occurrences of overdose must be reported as an SAE.

### Other Safety Considerations

Any significant worsening noted during interim or final physical examinations, electrocardiograms, x rays, and any other potential safety assessments, whether or not these procedures are required by the protocol, should also be recorded as a nonserious or serious AE, as appropriate, and reported accordingly.

### Funding Source Amgen Reporting Requirements:

Safety Data	Timeframe for Submission to Amgen
Suspected Unexpected Serious Adverse Reaction	Sent to Amgen at time of regulatory submission
Serious Adverse Events (SAEs)	Not required, unless contractually specified per study
Adverse Events not meeting serious criteria	Not required, unless contractually specified per study
Events of Interest	Not required, unless contractually specified per study
Pregnancy/Lactation	Within 10 calendar days of Sponsor awareness
Event listing for reconciliation	As specified per contract

\*Specific requirements are to be outlined in the Research Agreement

To report SUSPECTED ADVERSE REACTIONS, contact Amgen Inc. at [name]) or Food and Drug Administration (FDA) at [name] or [www.fda.gov/medwatch](http://www.fda.gov/medwatch).

**For all studies – aggregate reports\*:**

Safety Data	Timeframe for submission to Amgen
Annual Safety Report (eg, EU Clinical Trial Directive [CTD] Annual Safety Report, and US IND Annual Report)	Annually
Other Aggregate Analyses (any report containing safety data generated during the course of a study)	At time of ISS sponsor submission to any body governing research conduct (eg, RA, IRB, etc)
Final (End of Study Report, including: 

• Unblinding data for blinded studies

• Reports of unauthorized use of a marketed product

	At time of ISS sponsor submission to any body governing research conduct (eg, RA, IRB, etc) but not later than 1 calendar year of study completion

\*Specific requirements are to be outlined in the Research Agreement

**Bristol-Myers Squibb (BMS) Reporting Requirements**

For studies conducted under an Investigator IND in the US, any event that is both serious and unexpected must be reported to FDA as soon as possible and no later than 7 days (for a death or life-threatening event) or 15 days (for all other SAEs) after the investigator's or institution's initial receipt of the information. BMS will be provided with a simultaneous copy of all adverse events filed with the FDA.

[[contact]](mailto:[contact])

MedWatch SAE forms should be sent to the FDA at:

MEDWATCH

[name]

[name]

Fax: [name] ([name])

<http://www.accessdata.fda.gov/scripts/medwatch/>

All SAEs should simultaneously be faxed or e-mailed to BMS at:  
Global Pharmacovigilance & Epidemiology  
Bristol-Myers Squibb Company  
[contact]  
Email: [[contact]](mailto:[contact])

**FDA Expedited Reporting requirements for studies conducted under an IND:**

A sponsor (in this case the LCCC) must report any suspected adverse reaction that is both serious and unexpected to the FDA. The sponsor must report an adverse event as a suspected adverse reaction only if there is evidence to suggest a causal relationship between the drug and the adverse event, such as:

- A single occurrence of an event that is uncommon and known to be strongly associated with drug exposure (e.g., angioedema, hepatic injury, Stevens-Johnson Syndrome);
- One or more occurrences of an event that is not commonly associated with drug exposure, but is otherwise uncommon in the population exposed to the drug (e.g. tendon rupture);
- An aggregate analysis of specific events observed in a clinical trial (such as known consequences of underlying disease or condition under investigation or other events that commonly occur in the study population independent of drug therapy) that indicates those events occur more frequently in the drug treatment group than in a concurrent or historical control group.

The sponsor must submit each IND safety report on FDA Form 3500A. Each notification to FDA must bear prominent identification of its contents, i.e., “IND Safety Report,” and must be transmitted to the review division that has the responsibility for review of the IND. In each IND safety report, the sponsor must identify all IND safety reports previously submitted to FDA concerning a similar suspected adverse reaction, and must analyze the significance of the suspected adverse reaction in light of previous, similar reports or any other relevant information.

Timing

FDA must be notified of potential serious risks within 15 calendar days after the sponsor determines the event requires reporting. FDA must be notified of unexpected fatal or life-threatening suspected adverse reactions as soon as possible but in no case later than 7 calendar days after the sponsor’s initial receipt of the information. The sponsor must be notified by the investigator within 24 hours of the event. For Multicenter trials, Lineberger is the sponsor, therefore, the Multicenter Project Manager must be notified of the SAE within 24 hours of the event. If the results of a sponsor’s investigation show that an adverse event not initially determined to be reportable is reportable, the sponsor must report such suspected adverse reaction in an IND safety report as soon as possible, but in no case later than 15 calendar days after the determination is made.

Follow-up

The sponsor must promptly investigate all safety information it receives. Relevant follow-up information to an IND safety report must be submitted as soon as the information is available and as such the Multicenter Project Manager should be updated within 24 hours of the information being available via a follow-up MedWatch Form 3500A.

Notification of Investigators

The sponsor must notify all participating investigators (i.e., all investigators to whom the sponsor is providing drug under its INDs or under any investigator's IND) in an IND safety report of potential serious risks, from clinical trials or any other source, as soon as possible, but in no case later than 15 calendar days after the sponsor determines that the information qualifies for reporting.

Process

If the sponsor deems that an event is both a serious SAR AND unexpected, it must also (in addition to Oncore) be recorded on the MedWatch Form 3500A. Unexpected adverse events or adverse reaction refers to an event or reaction that is not listed in the investigator's brochure/IND or is not listed at the specificity or severity that has been observed; or if an investigator's brochure is not required or available, is not consistent with the risk information described in the general investigation plan or elsewhere in the current IND application.

The MedWatch 3500A form and supporting documents defining the event and causality should be sent to the electronic mailbox ([contact]; primary route of submission) (or [contact] (back-up)) of the Multicenter Project Manager along with supporting documentation defining the event and causality. The Multicenter Project Manager will then send the report to the Funding Source. The MedWatch 3500a form can be accessed at: <http://www.fda.gov/Safety/MedWatch/HowToReport/DownloadForms/default.htm>.

(Please be sure and access form 3500a, and not form 3500).

Once the UNC Principal Investigator determines an event is a serious SAR AND unexpected, the MedWatch 3500A form will be submitted to the FDA. If the event is serious, unexpected and considered to be possibly-, probably- or definitely-related to the study treatment, the Multicenter Project Manager will inform the Regulatory Associate at UNC and IND Specialist. The MedWatch form will be submitted according to LCCC SOP for safety reporting for a multi-site study.

All IND safety reports must be submitted on Form 3500A and be accompanied by Form 1571. The FDA must be notified of any unexpected or life-threatening suspected adverse reactions as soon as possible, but no later than 7 calendar days of learning of the event.

The Multicenter Project Manager will also be responsible for informing each Affiliate site of all serious and unexpected SARs reported to the FDA via fax as soon as possible.

#### Additional Reporting Requirements

The following additional items must be reported via IND safety report:

- *Findings from other studies.* The sponsor must report any findings from epidemiological studies, pooled analysis of multiple studies, or clinical studies, whether or not conducted under an IND, and whether or not conducted by the sponsor, that suggest a significant risk to humans exposed to the drug.
- *Findings from animal or in vitro testing.* The sponsor must report any findings from animal or *in vitro* testing, whether or not conducted by the sponsor, that suggest a significant risk in humans exposed to the drug, such as reports of mutagenicity, teratogenicity, or carcinogenicity, or reports of significant organ toxicity or near the expected human exposure.
- *Increased rate of occurrence of serious suspected adverse reactions.*

#### Additional Guidance

Please refer to 21CFR312.32 and “Guidance for Industry and Investigators: Safety Reporting Requirements for INDs and BA/BE Studies” for additional information and reporting requirements. All IND Safety Reports will be submitted in accordance with these regulations/guidances.

## **7.4 Data and Safety Monitoring Plan**

The Principal Investigator will provide continuous monitoring of subject safety in this trial with periodic reporting to the Data and Safety Monitoring Committee (DSMC).

Meetings/teleconferences will be held at a frequency dependent on study accrual, and in consultation with the study Biostatistician. These meetings will include the investigators as well as protocol nurses, clinical research associates, regulatory associates, data managers, biostatisticians, and any other relevant personnel the principal investigators may deem appropriate. At these meetings, the research team will discuss all issues relevant to study progress, including enrollment, safety, regulatory, data collection, etc.

The team will produce summaries or minutes of these meetings. These summaries will be available for inspection when requested by any of the regulatory bodies charged with the safety of human subjects and the integrity of data including, but not limited to, the oversight (Office of Human Research Ethics (OHRE) Biomedical IRB, the Oncology Protocol Review Committee (PRC) or the North Carolina TraCS Institute Data and Safety Monitoring Board (DSMB).

The UNC LCCC Data and Safety Monitoring Committee (DSMC) will review the study on a regular (quarterly to annually) basis, with the frequency of review based on risk and complexity as determined by the UNC Protocol Review Committee. The UNC PI will be responsible for submitting the following information for review: 1) safety and accrual data including the number of subjects treated; 2) significant developments reported in the literature that may affect the safety of participants or the ethics of the study; 3) preliminary response data; and 4) summaries of team meetings that have occurred since the last report. Findings of the DSMC review will be disseminated by memo to the UNC PI, PRC, and the UNC IRB and DSMB.

## 8.0 STATISTICAL CONSIDERATIONS

### 8.1 Study Design/Study Endpoints

This study will be a prospective, single arm, multicenter, open-label phase II clinical trial investigating the combination of nivolumab and ipilimumab with panitumumab in subjects with unresectable, refractory, *KRAS/NRAS/BRAF* wild-type, microsatellite stable metastatic colorectal cancer. The primary objective of this study is to estimate the ORR (CR + PR) in these subjects at 12 weeks by RECIST 1.1 criteria. Secondary objectives include the following: estimating the ORR (CR + PR) at 12 weeks by irRECIST criteria, estimating the best response rate by both RECIST 1.1 and irRECIST criteria, estimating PFS and duration of response using both RECIST 1.1 and irRECIST criteria, estimating OS, and characterizing the safety issues associated with this regimen. Exploratory objectives involve investigating various biomarkers and peripheral blood and tumor assays.

### 8.2 Sample Size and Accrual

Power and sample size considerations for this study are based on the primary objective. The historical overall response rate (CR+PR) of *KRAS* wild-type mCRC to panitumumab is approximately 22%. The proposed treatment regimen is expected to increase the response rate to a clinically relevant rate of at least 35%. A Simon two-stage minimax design will be used, with an  $\alpha=0.10$ , and power of 80%, to evaluate the efficacy of this treatment regimen. The null and alternative hypothesis overall response rates (CR + PR) are 22% and 35%, respectively. In the first stage, 32 evaluable subjects will be enrolled and treated. If 6 or less of these 32 first stage subjects are ‘responders’ (i.e., either a CR or a PR), the trial will be suspended and study investigators will consult with the study funding sources (BMS and Amgen) and with the DSMC about whether or not to continue accruing subjects to the study. However, if 7 subjects or more are found to be responders, another 24 evaluable subjects will be accrued for a total of at least 56 evaluable subjects. If a total of 17 (or more) responders are observed

among the total of 56 evaluable subjects, then this treatment regimen would be considered of clinical interest and therefore would justify further development.

We expect to accrue subjects at a rate of approximately 4 subjects per month. At this rate, we expect total accrual to this study to take approximately 30 months, allowing for up to 6 month assessment period for response between the first and second stages.

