## 1.0 BACKGROUND AND RATIONALE

### 1.1 Study Synopsis

We will conduct a single-arm, open-label Phase II clinical trial investigating the combination of nivolumab and ipilimumab with panitumumab in subjects with unresectable, refractory, *KRAS/NRAS/BRAF* wild-type, microsatellite stable (MSS) metastatic colorectal cancer (mCRC). There will be an initial safety lead-in cohort to ensure the combination is well-tolerated. The primary objective of this study is to estimate the overall response rate (CR + PR) in these subjects at 12 weeks by RECIST 1.1 criteria and also by irRECIST criteria. Secondary objectives include the following: estimating the overall response rate (CR + PR) in these subjects at 12 weeks by irRECIST criteria, estimating the best response rate by both RECIST 1.1 and irRECIST criteria, estimating PFS and duration of response using both RECIST 1.1 and irRECIST criteria, estimating OS, and characterizing the safety issues associated with this regimen. Exploratory objectives involve investigating various biomarkers and peripheral blood and tumor assays.

This treatment regimen will be of clinical interest if the objective response rate increases from the standard of care response rate of 22% with panitumumab alone to approximately 35% with combination therapy (adding nivolumab and ipilimumab to panitumumab).

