Currently, available biomarkers for CRC are limited to identifying subjects for whom certain treatment is not suited, rather than identifying those who may benefit from treatment. *KRAS* and *NRAS* mutation status provide a basis for subject selection regarding benefit from EGFR targeting antibodies as subjects with *KRAS* or *NRAS* mutations, which are detected in approximately 40% of CRCs, do not derive benefit from these treatments. There are no prognostic or predictive molecular markers for bevacizumab-based therapy which is directed against the vascular endothelial growth factor receptor (VEGF-R) pathway; moreover, due to the heterogeneous nature of CRC, a number of subjects receive little benefit or no benefit from these targeted agents. Although unique subtypes within CRC have been identified as shown in Table 1 below based on a consensus molecular subtyping strategy devised and recently reported by the Colorectal Cancer Subtyping Consortium, critical questions remain regarding the pathogenesis and biology of these tumors, and unfortunately, optimal biomarkers for evidence-based therapeutic approaches remain elusive. Key areas of unmet need include optimizing use of EGFR antibodies for *RAS/RAF* wild-type disease and improving treatment for subjects with *RAS* and *RAF* mutations where no proven targeted therapy exists.

Table 1. Proposed taxonomy of CRC reflecting significant biological differences in gene expression-based molecular subtypes (adapted from Nat Med 2015 21(11):1350-1356.)

CRC Molecular subtypes	CMS1 MSI Immune	CMS2 Canonical	CMS3 Metabolic	CMS4 Mesenchymal
Incidence	14%	37%	13%	23%
	Hypermutation MSI, Braf mutation Immune activation	MSS, CIN WNT/MYC pathway activation, TP53 mutation, EGFR amplification/overexpression	Low CIN Moderate WNT/MYC pathway activation, KRAS, PIK3CA and IGFBP2 mutation	CIN/MSI heterogeneous, Mesenchymal/TGF- beta activation, and NOTCH3/VEGFR2 overexpression
Prognosis	Worse survival After relapse			Worse relapse-free and overall survival

CIN = chromosomal instability; MSI= microsatellite instability; MSS  
microsatellite stable

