### 1.3 Panitumumab in CRC

Panitumumab is indicated for treatment of subjects with *KRAS* wild-type mCRC as monotherapy after disease progression after prior treatment with fluoropyrimidine, oxaliplatin, and irinotecan containing chemotherapy regimens. Panitumumab is a fully human IgG2 antibody that binds the EGFR. The EGFR and proteins involved in its downstream signal transduction play important roles in oncogenesis and tumor progression in CRC. EGFR is a transmembrane receptor tyrosine kinase that homodimerizes upon ligand binding to activate downstream intracellular signal transduction cascades, notably including the mitogen activated protein kinase (MAPK) pathway via RAS, RAF, and MEK, to ultimately promote cell proliferation and survival. There are three human RAS genes that encode homologous proteins, *HRAS*, *NRAS*, and *KRAS*. Mutations in codons 12 and 13 of *KRAS* are found in 37-43% of colorectal cancer subjects, and contribute to oncogenesis by driving cell proliferation in a growth factor-independent fashion. Panitumumab, administered at 6 mg/kg IV every 2 weeks, significantly improves progression-free survival (PFS) compared to best supportive care when administered to subjects with chemo-refractory mCRC whose tumors are wild-type in *KRAS* codons 12 and 13 (hazard ratio 0.45, 95% CI 0.34 to 0.59). After additional studies demonstrated that benefit with anti-EGFR therapy was limited to subjects whose tumors are wild-type in exons 2, 3, and 4 of *KRAS* and *NRAS*, consensus guidelines now recommend that only subjects who are wild-type on extended RAS testing receive anti-EGFR therapy. Additional studies have suggested that wild-type *BRAF* is also required for optimal response to anti-EGFR therapy. Thus, while panitumumab is effective for subjects with extended RAS and *BRAF* wild-type mCRC, the duration of benefit is limited, and so improving on panitumumab monotherapy with novel combination therapies is needed to extend the duration of benefit.

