## 2.4 Endpoints

### 2.4.1 Primary Endpoint

ORR is defined as the percentage of subjects with unresectable refractory *KRAS/NRAS/BRAF* wild-type MSS mCRC who achieve a complete response or a partial response (CR+PR) by 12 weeks to panitumumab/nivolumab/ipilimumab or panitumumab/nivolumab therapy per RECIST 1.1 criteria.

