### **3.0 SUBJECT ELIGIBILITY**

#### **3.1 Inclusion Criteria**

Subjects must meet all of the inclusion criteria as listed below to participate in this study.

- 3.1.1 Histologically or cytologically confirmed colorectal adenocarcinoma, with unresectable metastatic or locally advanced disease documented on diagnostic imaging studies.
- 3.1.2 Previously received 1-2 prior lines of therapy. Subjects who relapse within 6 months of adjuvant chemotherapy comprised of oxaliplatin and a fluoropyrimidine will have their adjuvant therapy count as one prior line of therapy.
- 3.1.3 Confirmed wild-type in KRAS and NRAS codons 12, 13, 59, 61, 117, and 146; and BRAF codon 600, by standard of care testing of tumor specimen. Tissue used for testing may have been collected from primary or metastatic site.
- 3.1.4 Microsatellite stable as detected by PCR-based assay OR CLIA-certified sequencing methodology such as Foundation One; OR mismatch repair proficient as detected by immunohistochemistry showing intact nuclear staining of MLH1, MSH2, MSH6, and PMS2.
- 3.1.5 Radiographically measurable disease present per RECIST 1.1

- 3.1.6** Age  $\geq$  18 years at the time of consent.
- 3.1.7** Eastern Cooperative Oncology Group (ECOG) performance status 0 or 1.
- 3.1.8** Blood counts performed within 3 weeks prior to starting study therapy must have absolute neutrophil count  $\geq$  1,500/mm^3, platelets  $\geq$  100,000/mm^3, and hemoglobin  $\geq$  9 g/dL.

**\*Note:** Hematology and other lab parameters that are  $\leq$  grade 2 BUT still meet criteria for study entry are allowed. Furthermore, changes in laboratory parameters during the study should not be considered adverse events unless they meet criteria for dose modification(s) of study medication outlined by the protocol and/or worsen from baseline during therapy.

- 3.1.9** Liver function tests performed within 3 weeks prior to starting study therapy must have total bilirubin  $\leq$  1.5 x upper limit of normal (ULN), alanine aminotransferase and aspartate aminotransferase  $\leq$  3 x ULN, and albumin  $\geq$  2.5 g/dL.
- 3.1.10** Serum creatinine performed within 3 weeks prior to starting study therapy must be  $\leq$  1.5 x ULN, or have calculated creatinine clearance (using Cockcroft-Gault formula provided in Appendix 11.3) of  $\geq$  50 mL/minute.

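### Does a 22% benchmark described for KRAS wild-type disease undermine the 17/56 rule in a KRAS/NRAS/BRAF wild-type trial?

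*Combined protocol and SAP*

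**What the plan says.** Section 8.2 (Sample Size and Accrual) states: "The historical overall response rate (CR+PR) of *KRAS* wild-type mCRC to panitumumab is approximately 22" percent. It gives no reference. From this it takes null and alternative rates of 22% and 35%, a Simon two-stage minimax design, alpha 0.10 and power 80%. With 6 or fewer responders among the first 32 evaluable subjects, accrual is suspended for consultation. With 7 or more, a further 24 are enrolled. A total of 17 or more responders among 56 makes the regimen of clinical interest. Section 1.1 repeats the figure as "the standard of care response rate of 22% with panitumumab alone", with no KRAS qualifier and again no reference.

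Section 3.1.3 requires tumours "Confirmed wild-type in KRAS and NRAS codons 12, 13, 59, 61, 117, and 146; and BRAF codon 600". Section 2.4.1 counts subjects "who achieve a complete response or a partial response (CR+PR) by 12 weeks".

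The background supports an effect of molecular selection. Section 1.2 says that subjects with KRAS or NRAS mutations, "which are detected in approximately 40% of CRCs, do not derive benefit from these treatments". Section 1.3 says that "benefit with anti-EGFR therapy was limited to subjects whose tumors are wild-type in exons 2, 3, and 4" of KRAS and NRAS, and that studies suggest wild-type BRAF "is also required for optimal response to anti-EGFR therapy".

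**The concern.** The benchmark is worded for one population and the trial enrols a more selected one. If the 22% came from patients tested for KRAS alone, that group would include some NRAS and BRAF mutants who, on the protocol's own account, gain little or nothing from an anti-EGFR antibody. Leaving them out would raise the panitumumab-alone rate. With no concurrent control, a result of 17/56 can be read as a gain over panitumumab only through this benchmark. If the matched rate were above 22%, a regimen that adds nothing would pass more often than the stated 10%, and part of a positive result would reflect selection. The margin is also thin, as the calculation shows.

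**Working it through.** **Inputs.** p0 = 0.22, p1 = 0.35, n1 = 32 (continue with 7 or more), N = 56 (pass with 17 or more), all from Section 8.2. KRAS codon 12/13 mutations "are found in 37-43% of colorectal cancer subjects" (Section 1.3). KRAS or NRAS mutations in about 40% (Section 1.2). Response by 12 weeks (Section 2.4.1).

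**1. Reproducing the plan.** P(pass | p) is the sum over x = 7 to 32 of Bin(x; 32, p) × P(Bin(24, p) ≥ 17 − x).

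- At p = 0.22: 0.0903.
- At p = 0.35: 0.8012.

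A full minimax search for 22% against 35%, alpha 0.10 and power 80%, returns the same design. Stage 1 only suspends accrual. If it is ignored altogether, the figures are 0.0919 and 0.8064.

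**2. Margin.** Solving P(pass | p) = 0.10 gives p = 0.2231 (0.2225 with stage 1 ignored). A group containing 1 − 0.22/0.2231 = 1.4% non-responding mutants would be enough to use it up, other things equal.

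**3. How large an excess do the documents support?** Suppose every responder is KRAS/NRAS wild-type. Let k be the share with KRAS codon 12/13 mutations and m the share with any KRAS or NRAS mutation. The rate in the KRAS/NRAS wild-type group is then 0.22 × (1 − k)/(1 − m).

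- k = 0.43: 0.22 × 0.57/0.60 = 0.209.
- k = 0.40: 0.22 × 0.60/0.60 = 0.220.
- k = 0.37: 0.22 × 0.63/0.60 = 0.231.

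Values below 0.22 are impossible under this assumption, because the enrolled group is a subset of KRAS wild-type. That leaves 22.0% to 23.1%, with pass probabilities of 0.090 to 0.128. That the formula can fall below 22% at all shows that the two mutation figures are too approximate to resolve a difference of one percentage point. BRAF would add to the rate, but the documents give no size for it.

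**4. The 12-week window.** If the 22% is a best response over any period, only the part reached by 12 weeks is comparable with the endpoint. Assume that part is 80% to 90%; the documents give no figure.

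| Rate before offset | Rate by 12 weeks | P(pass) |
|---|---|---|
| 22.0% | 17.6-19.8% | 0.013-0.039 |
| 23.1% | 18.5-20.8% | 0.021-0.058 |

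To bring 23.1% down to the 22.31% limit, only 1 − 22.31/23.1 = 3.4% of responses need to come after week 12.

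**5. Larger benchmarks, for illustration.** P(pass) is 0.214 at 25%, 0.328 at 27% and 0.521 at 30%. No section gives a panitumumab rate at any of these levels.

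**The case for a change.** The strongest case for acting is that the background itself says the two populations differ on the feature that governs response to the comparator, while the rule has a margin of only 0.3 percentage points. The word for approximately in Section 8.2 covers more than that. A citation and one conditional sentence would cost no patients. The mismatch in wording, the missing reference and the thin margin all stand.

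Three further arguments do not carry the point.

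- Section 1.5 puts the KRAS/NRAS wild-type share of MSS metastatic disease at 40-50%. Used as the denominator, this gives 0.22 × 0.57/0.50 = 25% up to 0.22 × 0.63/0.40 = 35%. But it sets a KRAS frequency from colorectal cancer in general against a wild-type share from MSS metastatic disease, so the ratio is not like for like.
- The planned Wilson 95% interval at 17/56 is 19.9% to 43.3% and includes 22%. That is a two-sided 95% interval beside a one-sided 10% test. The matching 80% interval is 23.1% to 38.7% and excludes 22%. Neither bears on molecular selection.
- The final cut-off could be raised. For a benchmark of 25%, 19/56 gives an error of 0.085, but power at 35% falls from 0.801 to 0.615. That is a heavy price to guard against a rate the documents do not give.

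**Conclusion.** The concern does not call for a change. The design is correct for the rates it states, and every single-arm trial has an error rate that depends on its historical benchmark. Whether 22% is too low here is not settled: molecular selection tends to raise the matched rate, the 12-week window may lower it, and the one like-for-like estimate moves the error from 9.0% to at most 12.8% before any offset or BRAF effect. KRAS in Section 8.2 may also be shorthand, since Section 1.1 gives the same 22% as standard of care for panitumumab alone and Section 1.3 reports that guidelines now limit anti-EGFR therapy to extended RAS wild-type tumours.

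The missing source is a gap in documentation. Supplying it would alter neither the sample size, the stopping bound nor the analysis, and whoever reports the trial will have to set the result against published panitumumab rates in any case. Section 8.2 treats 17/56 as grounds for further development, not as proof of superiority, and a provisional benchmark is adequate for that decision.

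This rests on two assumptions: that all responders are RAS wild-type, and that the 22% is a best response with some responses after week 12. A sourced panitumumab rate by 12 weeks in KRAS/NRAS/BRAF wild-type disease clearly above 22.3% would reopen the question.
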